2. *on-treatment period*: from date of first administration of study treatment to 30 days after date of last actual administration of any study treatment (including start and stop date)
3. *post-treatment period*: starting at day 30 + 1 after last administration of study treatment

If a clear assignment to the pre-, on-, or post-treatment period cannot be made, e.g., in case of specific incomplete dates, then the respective data will be assigned to the on-treatment period.

Safety summaries (tables, figures) include only data from the on-treatment period with the exception of baseline data which will also be summarized where appropriate (e.g. change from baseline summaries). In addition, a separate summary for death including on-treatment and post-treatment deaths will be provided. In particular, summary tables for adverse events (AEs) will summarize only on-treatment events, with a start date during the on-treatment period (*treatment-emergent* AEs).

However, all safety data (including those from the post-treatment period) will be listed and those collected during the pre-treatment and post-treatment period will be flagged.

Windows for multiple assessments

In order to summarize ECG data collected over time (including unscheduled visits), the assessments will be time slotted. The following general rule will be applied in creating the assessment windows: If more than 1 assessment is done within the same time window, the assessment performed closest to the target date will be used. If 2 assessments within a time window are equidistant from the target date, then the earlier of the 2 assessments will be used. If multiple assessments occur on the same date then the worst case will be used except for ECGs. Three ECGs are targeted to be measured at the protocol-defined (nominal) time-points. If a subject has more than one measurement at a specific time point, the average of all available measurements associated with the nominal time point will be used for the analysis. Data from all assessments (scheduled and unscheduled), including multiple assessments, will be listed.

Last contact date

The last contact date will be derived for subjects not known to have died at the analysis cut-off [REDACTED] using the last complete date among the following.

Table 2-1 Last contact date data sources

Source data	Conditions
Last known date patient alive collected on the 'Survival information' eCRF	Subject status is reported to be unknown or lost to follow-up

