Date of assessment collected on the 'Survival information' eCRF	Subject status is reported to be alive and missing last known date patient alive
Start/end dates of anti-neoplastic therapies administered after study treatment discontinuation	Non-missing medication or procedure term
Study medication start/end dates from DAR eCRF	Non-missing dose; zero doses are allowed
Date of discontinuation from 'End of Treatment' eCRF and 'End of post-treatment phase' eCRF	None
Start/End dates of AE	Non-missing verbatim AE term
Tumor (RECIST) assessment date	Evaluation is marked as 'done'
Laboratory/PK collection dates	Sample collection marked as 'done'
Vital signs, ECG assessment dates	At least one non-missing parameter value
Performance status dates	Non-missing performance status

The last contact date is defined as the latest complete date from the above list or the cut-off date whichever comes first. The cut-off date will not be used for last contact date, unless the subject was seen or contacted on that date. No date post cut-off date will be used. Completely imputed dates (e.g. the analysis cut-off date programmatically imputed to replace the missing end date of a dose administration record) will not be used to derive the last contact date. Partial date imputation is allowed for event (death)/censoring if coming from 'Survival information' eCRF.

The last contact date will be used for censoring of subjects in the analysis of overall survival.

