4. Visit date of study treatment discontinuation or end of post-treatment follow-up discontinuation due to lost to follow-up

Then the PFS censoring reason will be:

1. 'Ongoing'
2. 'New cancer therapy added'
3. 'Withdrew consent'
4. 'Lost to follow-up'

If the time interval is larger than the interval of 2 missing TAs with no event observed, then the PFS censoring reason will always default to 'Adequate assessment no longer available'. If the time interval between the last adequate TA date and the PFS event date is larger than the interval of 2 missing TAs then the subject will be censored and the censoring reason will be 'Event documented after two or more missing tumor assessments'.

These summaries on censoring reasons will be produced for PFS by investigator assessment and BIRC assessment.

Censoring pattern of OS

The pattern of censored data will be examined regarding reasons for censoring ('Alive' or 'Lost to follow-up'). In addition, survival status, reason for censoring and cause of death will be listed.

Subgroup analyses for secondary efficacy endpoints

For the secondary efficacy endpoints the following subgroup analyses will be prepared.

The ORR and DCR summaries based on investigator and BIRC assessment will be analyzed by T790M mutation status and MET dysregulation status for Phase Ib subjects. Overall survival will be analyzed by MET dysregulation status.

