Treatment discontinuation due to ‘Disease progression’ without documented progression, i.e. clinical progression based on investigator claim	Date of last adequate assessment	Censored
New anti-cancer therapy given prior to protocol defined progression	Date of last adequate assessment on or prior to starting new anti-cancer therapy	Censored
Death before first PD assessment	Date of death	Progressed

OS

If a subject is not known to have died at the time of the analysis, then OS time will be censored at the date of last known date subject was alive, i.e., last contact date (see [Section 2.1.4](#)). If the tick box for ‘Lost to follow-up’ is ticked on the ‘Survival information’ eCRF or if the time between the last contact date and the [REDACTED] analysis cut-off date is longer than the protocol specified interval between the survival follow-up assessments plus 2 weeks, i.e., 15 weeks for this study ($3 \times 30.4375 + 14 \text{ days} = 91.3125 + 14 \text{ days} = 105.3125 \text{ days} \approx 15 \text{ weeks}$), subjects OS time will be censored for ‘Lost to follow-up’.

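### Table 2-1 counts discontinuation dates as last contact with no condition, so subjects lost to follow-up can gain OS time in which a death would go unseen

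*SAP*

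**What the plan says.** Table 2-1 in SAP Section 2.1.4 lists the sources for the last contact date, each with a condition. One row is "Date of discontinuation from 'End of Treatment' eCRF and 'End of post-treatment phase' eCRF", and its condition is 'None'.

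The selection rule is "The last contact date is defined as the latest complete date from the above list or the cut-off date whichever comes first". Its purpose is also stated: "The last contact date will be used for censoring of subjects in the analysis of overall survival". Section 2.7.3 gives the intended meaning of that censoring time: "OS time will be censored at the date of last known date subject was alive".

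Three neighbouring rules are stricter:
- The last known alive date on the Survival information page is used under the condition "Subject status is reported to be unknown or lost to follow-up".
- The assessment date on that page is used only under the condition "Subject status is reported to be alive and missing last known date patient alive".
- For the cut-off itself, "The cut-off date will not be used for last contact date, unless the subject was seen or contacted on that date".

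In Section 2.7.2, the PFS censoring reasons use the date described as "Visit date of study treatment discontinuation or end of post-treatment follow-up discontinuation due to lost to follow-up". So the SAP recognises that a subject can leave the treatment phase or the post-treatment phase because contact was lost.

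**The concern.** A discontinuation date shows that a subject was alive only if someone saw or reached the subject on that day. When the reason is loss to follow-up, that cannot be assumed. Table 2-1 takes the latest date, so a later discontinuation date overrides every earlier real contact, including a last known alive date entered on the Survival information page. The bars on post-cut-off dates and on completely imputed dates do not reach a complete date before the cut-off, and no other rule in the SAP text excludes it.

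Two results could be affected. A subject carried past the last real contact stays in the OS risk set while a death in that stretch would go unseen, which pushes the Kaplan-Meier estimate up. The OS censoring summary ('Alive' or 'Lost to follow-up') can also change, because one of its two criteria is the time from last contact to cut-off.

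**Working it through.** **The SAP's own figure.** The window in Section 2.7.3 is 3 × 30.4375 + 14 = 91.3125 + 14 = 105.3125 days. Divided by 7 this is 15.04 weeks, so the stated 15 weeks reproduces.

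**Effect on one subject.** Let *v* be the last real contact, *d* the recorded discontinuation date and *c* the cut-off, with *d* no later than *c*. If no other source is later than *d* and no death is known, OS is censored at *d* instead of *v*, a gain of *d* − *v* days. At each death time in that interval the Kaplan-Meier factor becomes 1 − 1/(n + 1) instead of 1 − 1/n, where n is the number at risk without this subject. The estimate can only rise. If *d* = *v*, nothing changes.

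**Effect on the label.** Section 2.7.3 labels the subject lost if the box on the Survival information page is ticked, or if last contact lies more than 105.3125 days before cut-off. The label therefore moves to 'Alive' only if all three hold: the box is not ticked, *c* − *v* > 105.3125, and *c* − *d* ≤ 105.3125.

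**Size.** The SAP gives no loss rate, delay or expected OS, so these are assumptions. Both settings use n = 40 (the minimum for Group 3 in Section 1.1.2), exponential OS and 4000 simulated trials per scenario.

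Setting A has median OS 20 months and follow-up of 24 to 48 months:
- 10% lost, 3-month delay: 24-month OS 0.434 → 0.438 (+0.4 points); median 20.3 → 20.5 months (+0.2).
- 20% lost, 6-month delay: 24-month OS 0.435 → 0.454 (+1.9 points); median 20.5 → 21.5 months (+1.0).

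Setting B has median OS 24 months, follow-up of 48 months, and loss times uniform over 0 to 24 months among the share assigned to loss. Some of these die before they are lost, so fewer are actually lost:

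| Share assigned to loss | Mean lost of 40 | 24-month OS, delay 0 | delay 105 days | delay 180 days | Rise in points (105 / 180 days) |
|---|---|---|---|---|---|
| 5% | 1.4 to 1.5 | 0.4995 | 0.5004 | 0.5036 | 0.1 / 0.4 |
| 10% | 2.9 | 0.5009 | 0.5050 | 0.5091 | 0.4 / 0.8 |
| 20% | 5.8 | 0.5018 | 0.5119 | 0.5169 | 1.0 / 1.5 |

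The medians at delays of 0, 105 and 180 days are:
- 5%: 24.17, 24.16 and 24.31 months.
- 10%: 24.47, 24.64 and 24.95 months.
- 20%: 24.66, 25.31 and 25.61 months.

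The largest rise in the median is 25.61 − 24.66 = 0.95 months.

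**Simulation noise in setting B.** The standard error of one mean is about √(0.5 × 0.5/40)/√4000 = 0.00125. For a difference of two independent means it is 0.00125 × √2 = 0.0018, or about 0.2 points. The 5% row is therefore barely distinguishable from zero.

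**Comparison with sampling error.** At 24-month OS of 0.435 and n = 40, the approximate 95% half-width is 1.96 × √(0.435 × 0.565/40) = 0.154, or about 15 points, ignoring earlier censoring. The largest rise above is about an eighth of that (1.9/15.4).

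**The case against.** The strongest objection is that the SAP never says what the date means for a lost subject. A reader might infer that it is the day the site gave up. The documents do not support that: Section 2.7.2 calls it a visit date, and a visit date would leave no unobserved time. The SAP's change log refers to eCRF completion guidelines, which are not part of the document and may settle the matter. This stands. It makes the gain possible, not established.

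A reader might also infer that every other row of Table 2-1 demands proof of contact. It does not. Dosing dates count with a zero dose, AE dates need only a verbatim term, and post-treatment therapy dates need only a medication or procedure term. What remains true is that this row alone has no condition, and that the Survival-page rows and the cut-off rule do guard against this problem.

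Few subjects can be affected. A later contact in survival follow-up supersedes the discontinuation date, and a known death removes the subject from the derivation. A ticked 'Lost to follow-up' box protects the label, though not the censoring date.

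Finally, OS is a secondary, descriptive endpoint in a study without randomisation, and the possible shift is far inside the sampling error. That settles the priority. It is no reason to leave the row open when the neighbouring rows are conditioned.

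**Conclusion.** The point holds as a gap in the rule. The unconditioned row can set the OS censoring date later than the day the subject was last known alive, against Section 2.7.3, for subjects whose discontinuation was due to loss to follow-up. Any bias is upward and small: about 0 to 2 points on 24-month OS and 0 to 1 month on the median. That range rests on an assumed 5% to 20% lost, delays of up to about six months, and exponential OS with a median of 20 or 24 months. It is zero if sites enter the true last contact date.

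The label can change only under the three joint conditions shown in the working. The documents do not support the stronger conclusion that the OS results are biased, because neither the site practice nor the number of lost subjects is given. This is a minor improvement to the specification.

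**What to change.** In Table 2-1, replace 'None' in this row with: *Reason for discontinuation is not lost to follow-up, or the subject was seen or contacted on that date.* Otherwise take the last contact date from the other sources in the table. Every FAS subject has received at least one dose (Section 2.2), so a dosing date should ordinarily exist as a fallback.

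The second clause matters. Excluding the date for all lost subjects would discard real contacts, such as a telephone call that no other row records.

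The cost is one table cell and one filter in the derivation program. The downside is slightly shorter OS follow-up for a few subjects. A count of subjects whose last contact date comes from this row and whose reason is loss to follow-up would show at once whether anyone is affected.

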2.2 Analysis sets

Full analysis set

The Full analysis set (FAS) comprises all subjects who have received at least one dose of either INC280 or EGF816. Subjects will be analyzed according to the planned treatment they have been assigned to.

Safety set

The Safety set includes all subjects who received any study treatment (i.e. at least one dose of any component of the study treatment). Subjects will be analyzed according to the study treatment (regimen) they actually received.

The actual treatment received corresponds to:

- the assigned treatment if subjects took at least one dose of that treatment
- the first treatment received if the assigned treatment was never received

Each subject will be classified into and analyzed consistently within one (and only one) combination treatment group.

2.2.1 Subject classification

Subjects may be excluded from the analysis sets defined above based on the protocol deviations (PDs) entered in the database and/or on specific subject classification rules defined in [Table 2-2](#).

Table 2-2 Subject classification based on protocol deviations and non-PD criteria

Analysis set	Protocol deviations leading to exclusion	Non protocol deviation leading to exclusion
FAS	No written informed consent – INCL01	–
Safety set	No written informed consent – INCL01	–

Withdrawal of informed consent

Any data collected in the clinical database after a subject withdraws informed consent from all further participation in the trial, will not be included in the analysis data sets. The date on which a subject withdraws full consent is recorded in the eCRF.

Additional data for which there is a separate informed consent, e.g. biomarker, collected in the clinical database without having obtained that consent will not be included in the analysis. These data will be excluded by the presence of the appropriate protocol deviation criterion.

2.2.2 Subgroups of interest

The following subgroups will be used in analyses of efficacy.

2.2.2.1 Resistance mechanism to EGFR TKI treatment

Three subgroups will be considered regarding the acquired resistance mechanism to EGFR TKI treatment, based on the acquired T790M mutation status, the MET dysregulation status, and both combined.

For subjects in Phase Ib the subgroup category will be derived from the biomarker results. Details are given in [Section 2.11.5](#).

For subjects in Phase II the subgroup category is collected in the IRT system [REDACTED]. For the subgroup classification, the biomarker results will be used similar to the Phase Ib case, see [Section 2.11.5](#). The subgroups will be summarized by means of a frequency table (T790M & MET status) and a contingency table (MET dysregulation status vs T790M mutation status) by treatment group. Percentages will be calculated using the number of subjects in the relevant analysis set or subgroup as the denominator.

The subgroups will mainly be used in analyses for the Phase II Group 1. In addition, some analyses for Phase Ib subjects will also be prepared by these subgroups.

Subjects in Phase II Group 3 and Group 4 also have subgroup categories collected in the IRT system. These will only be presented in a listing.

T790M & MET status

- T790M+, MET dysregulation– (Group 1 subgroup a)
- T790M–, MET dysregulation+ (Group 1 subgroup b)
- T790M+, MET dysregulation+ (Group 1 subgroup c1)
- T790M–, MET dysregulation– (Group 1 subgroup c2)
- Other/Unknown (Group 1 subgroup c3)

T790M mutation status

- T790M positive (or short T790M+): subjects with T790M mutation present (Group 1 subgroup a or c1)
- T790M negative (or short T790M–): subjects without acquired mutation T790M (Group 1 subgroup b or c2)
- T790M unknown (or short T790M?): subjects with unknown T790M status (Group 1 subgroup c3)

MET dysregulation status

- MET dysregulated: subjects whose tumor sample analysis shows
 - IHC 3+ (defined as $\geq 50\%$ of cells staining with high intensity) and/or
 - MET gene copy number ≥ 4(Group 1 subgroup b or c1)
- MET not dysregulated: subjects without MET dysregulation as defined above (Group 1 subgroup a or c2)

2.2.2.2 Subjects with CNS metastases

The presence or absence of CNS metastases (CNS mets) will be identified from the lesion locations (RECIST eCRF page) at baseline [REDACTED].

- Category ‘CNS mets present’: subjects whose lesion locations contain one or more of the following values (case insensitive)

BRAIN
BRAIN STEM
CEREBELLUM
CEREBRAL CORTEX
CEREBRUM
CERVICAL SPINE
CNS - NOT OTHERWISE SPECIFIED
CNS: SUPRATENTORIAL
CNS: INFRATENTORIAL
CORPUS CALLOSUM
FRONTAL
LEPTOMENINGEAL
LUMBAR SPINE
OCCIPITAL
PARIETAL
PITUITARY
PONS
SPINAL CORD
TEMPORAL
THALAMUS
THORACIC SPINE
WHOLE BRAIN

- Category ‘CNS mets absent’: will be assigned to all other subjects

For outputs based on the investigator assessment, identification of CNS metastases at baseline will use the data from the investigator review. For outputs based on the BIRC assessment, identification of CNS metastases at baseline will use the data from the BIRC review.

The number of subjects with CNS metastases in target lesions, non-target lesions, and new lesions as well as the responses on target lesions and non-target lesions will be summarized based on investigator and BIRC assessment, respectively.

The CNS metastases subgroups will be used for efficacy analyses of ORR, DOR and PFS.

Note: metastatic sites data collected in the Diagnosis and Extent of Cancer eCRF page will not contribute to the subgroup derivation.

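### The code list for CNS metastases includes three spine regions, so as written a vertebral bone lesion alone places a subject in the CNS subgroup

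*SAP*

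**What the plan says.** Under SAP Section 2.2.2.2, CNS metastases "will be identified from the lesion locations (RECIST eCRF page) at baseline"; the text directly after this is redacted. The category 'CNS mets present' goes to "subjects whose lesion locations contain one or more of the following values (case insensitive", followed by 22 values. Among them are "CERVICAL SPINE", "THORACIC SPINE" and the lumbar spine. The spinal cord is a separate entry, and so is "LEPTOMENINGEAL". The category 'CNS mets absent' "will be assigned to all other subjects".

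The section sets the use of the label: "The CNS metastases subgroups will be used for efficacy analyses of ORR, DOR and PFS". It also plans summaries of CNS metastases among target, non-target and new lesions, and of target and non-target responses. The investigator's lesion locations serve the investigator-based outputs and the BIRC's serve the BIRC-based outputs. A closing note adds that "metastatic sites data collected in the Diagnosis and Extent of Cancer eCRF page will not contribute to the subgroup derivation".

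**The concern.** The cervical, thoracic and lumbar spine are regions of the vertebral column. A lesion recorded there may be a bone metastasis with no involvement of cord or meninges. Disease of the cord and the leptomeninges already has its own entries, so the spine values are not needed to capture it when it is coded that way. What they visibly add is the vertebral lesion.

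At stake is what the 'CNS mets present' results describe. Any bone-only subject in that subgroup makes its ORR, DOR and PFS describe a mixture, and its size overstates how many subjects had CNS disease. The lesion summaries carry the same error if they use this list, which is the only CNS definition in the section. No planned output visible in the SAP shows who qualified on a spine value alone, so a reader of the report could not see the effect.

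**Working it through.** The SAP gives no count, sample size or precision for this subgroup, so there is no stated figure to reproduce. The check has two parts.

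**1. The rule against the rest of the SAP**

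- *List content.* There are 22 values: three vertebral-column regions, one cord value and one leptomeningeal value among them. Without the three spine values, 19 remain, and the cord and leptomeningeal values are still there.
- *Sufficiency.* One listed value is enough. The visible rule does not ask for the tissue or organ class.
- *Bone and CNS elsewhere.* Sections 2.5.2.1 and 2.5.2.3 name radiotherapy to bone and to the CNS as separate items. The SAP thus treats them as different sites.
- *Cross-check.* Section 2.3.1 takes the baseline table of metastatic sites from the Diagnosis and Extent of Cancer page, which Section 2.2.2.2 bars from the derivation. One report could therefore show a subject with bone and no CNS disease at baseline and as 'CNS mets present' in the efficacy tables.
- *Two readers, one list.* The same list applies to investigator and BIRC data, so agreement between the two would not reveal the problem.

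**2. Illustration of size**

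Inputs:

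- n = 40, the minimum for Group 3 in Section 1.1.2.
- c = share of subjects with true CNS disease, 20% to 40% (assumption).
- s = share of the remaining subjects with a spine-coded lesion, 5% to 20% (assumption).

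Formulas: true = n × c; false = n × (1 − c) × s; false share of 'present' = false / (true + false).

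| c | s | True | False | False share |
|---|---|---|---|---|
| 20% | 5% | 8.0 | 1.6 | 17% |
| 20% | 10% | 8.0 | 3.2 | 29% |
| 20% | 20% | 8.0 | 6.4 | 44% |
| 30% | 5% | 12.0 | 1.4 | 10% |
| 30% | 10% | 12.0 | 2.8 | 19% |
| 30% | 20% | 12.0 | 5.6 | 32% |
| 40% | 5% | 16.0 | 1.2 | 7% |
| 40% | 10% | 16.0 | 2.4 | 13% |
| 40% | 20% | 16.0 | 4.8 | 23% |

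Central case: 40 × 0.70 × 0.10 = 2.8 false against 40 × 0.30 = 12 true, and 2.8 / 14.8 = 19%.

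Effect on a rate: suppose ORR is 40% with and 60% without CNS disease (assumption), and falsely labelled subjects respond like the others without CNS disease. The labelled subgroup then shows 0.40 + 0.20 × false share. That gives 41% at a false share of 7%, 44% at 19% and 49% at 44%, instead of 40%.

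**The case against.** The strongest reply is that the eCRF and BIRC location dictionaries are not shown. If vertebral bone lesions carry a bone code and the spine values are reserved for intraspinal lesions, nobody is misclassified. The redacted text after the data source could also hold a qualifier. This stands as a limit on certainty and size. It does not clear the rule, because nothing visible says so and the separate cord entry makes that reading less likely.

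It is also fair that these subgroup results are descriptive. Section 2.5.2.2 reports ORR with exact intervals, no visible text ties a hypothesis or decision to CNS status, and individual lesion data are listed by subject. This limits the consequence but does not correct the definition.

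A reader might infer three stronger points that the SAP does not support:

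- *Substring matching.* One could read 'contain' as a text search, so that the parietal or frontal entries also catch pleural or skull sites. The list has brain, brain stem and whole brain as separate entries, two of which would be redundant under a text search. The natural reading is that a subject's recorded locations include a listed coded value. Nor does the SAP show that any pleural or skull value exists in the dictionary.
- *Both subgroups mislabelled.* The error runs one way, from 'absent' into 'present'. The 'absent' group loses members, but this defect does not mislabel those who stay.
- *A large loss of contrast between the subgroups.* The SAP gives no subgroup counts or rates, so any such figure comes from the assumptions chosen.

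**Conclusion.** The concern holds as a defect in a subgroup definition. Taken at its word, Section 2.2.2.2 classes a subject with only a vertebral bone lesion as having CNS metastases, in analyses the SAP presents as describing CNS disease.

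The number affected is unknown and may be nil. The illustrated range of about 1 to 6 subjects in 40, central case about 3, rests wholly on the assumed shares c and s and on the spine values being used for bone lesions. In a subgroup this small, two or three misplaced subjects can move an estimate.

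The primary ORR analysis by group and the Group 4 safety analysis do not use the label and are untouched. The point merits a correction to the SAP; it does not threaten the trial's main conclusions.

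**What to change.** In Section 2.2.2.2, either remove the three spine values, or count them only when the lesion record identifies cord, intradural or leptomeningeal disease. Under either option, report for investigator and BIRC data separately how many subjects qualify on a spine value alone. If that number is zero, the results stand and a footnote is enough. Use the corrected list for the CNS lesion summaries as well.

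The edit is one change to a code list and one added count. It has three costs:

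- The 'present' subgroup may become smaller and its intervals wider.
- Outright removal would lose a true intraspinal lesion recorded only by spine region. The conditional option avoids this but needs a look at the lesion records.
- The amendment history shows that a CNS definition was added before the Group 3 primary analysis. If earlier reports used the same list, a footnote should explain the change and its effect on comparability.
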